12.5. End of Study

The end of study is when 100 subjects complete the 1-year safety and cellulite severity evaluations. At the time of study termination, ongoing subjects receiving treatment will be followed through the Day 71 visit. The remaining enrolled subjects (in excess of the first 100 subjects to complete 1 year) will undergo early termination procedures in accord with the Schedule of Events (section [5](#)).

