14.5. Reporting Adverse Events and Serious Adverse Events

14.5.1. Reporting Adverse Events

Throughout the study, AEs will be documented on the source document and on the appropriate page of the eCRF whether or not considered treatment-related. This includes any new signs, symptoms, injury or illness, including increased severity of previously existing signs, symptoms, injury, or illness. Conditions existing prior to screening will be recorded as part of the subject's medical history. The Investigator is responsible for assessing the relationship of AEs to the study medication; relationship will be classified as not related, unlikely related, possibly related, or probably related.

All AEs will be collected by the Investigator from the time of signing the informed consent through 30 days after the last dose of study medication; this includes any AEs that are ongoing at the time of completion/termination of the study. All ongoing AEs must be followed until resolution or for 30 days after the subject's last study visit, whichever comes first.

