17.6. Safety Analyses

The following variables are safety endpoints.

- AEs: Mapped to preferred term using the Medical Dictionary for Regulatory Activities (MedDRA)
- Injection site reactions/local tolerability in selected quadrant (through subject and Investigator reporting)
- Vital signs
- Laboratory testing

AEs will be summarized by treatment group. AE duration will be summarized using descriptive statistics by treatment group.

Descriptive statistics will be presented for each clinical laboratory test for the actual and change from screening at each visit by treatment group and vital signs for the actual and change from Day 1 pre-injection for each injection day at each visit by treatment group.

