3. STATISTICAL METHODS AND CONSIDERATIONS

3.1. Descriptive Statistics

All analysis results will be presented in summary table using appropriate descriptive statistics, unless otherwise stated. The statistics include the number (count) and percentage for all categorical variables. The denominator will be based on the number of subjects in each column group in the summary table, unless otherwise stated. All continuous variables will be summarized with observed count, mean, standard deviation, median, minimum, and maximum value.

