7.4. Adverse Events

Treatment-emergent adverse events (TEAEs) is defined as any AE with onset date on or after the treatment start date in each treatment course in study EN3835-202. TEAEs are defined within each treatment course in study EN3835-202. AEs with missing or partial onset date and cannot be determined in which treatment course it occurred with its onset and end dates will be considered as TEAEs in treatment course 1. AEs with missing or partial onset date and cannot be determined in which treatment session it occurred with its onset and end dates will be considered as earliest treatment course and earliest treatment session possible.

Treatment-related adverse events are TEAEs with a relationship to study medication of possible, probable, or missing.

AEs will be coded using the Medical Dictionary for Regulatory Activities (MedDRA), Version 19.0.

Overall AE summaries for observation phase as well as overall TEAE summaries for treatment phase will be tabulated. Descriptive statistics (the number and percentage) for subjects reporting AEs, TEAEs, and Adverse Events of Special Interest (AESI) will be tabulated by system organ class (SOC) and preferred term (PT); by SOC, PT, and severity; and by SOC, PT, severity and relationship to study drug. TEAE will also be summarized by SOC, PT, and treatment course. The duration of treatment related AE descriptive statistics will be summarized within each PT under each SOC. The TEAE tables will be sorted by SOC and PT in decreasing frequency of the number of subjects in the overall column.

If there are more than 1 AE coded to the same SOC or PT for the same subject under a certain column in the summary table, the subject will be counted only once for that SOC or PT under that column. If there are more than 1 AE coded to the same PT for the same subject, the subject will be counted only once for that PT using the most severe and most related occurrence for the summarization by severity and by relationship to the study drug. If there are more than 1 AE coded to the same PT, the longest AE will be used for that PT for the duration descriptive statistics.

Serious adverse events (SAEs) and AEs leading to premature discontinuation of study drug will be summarized. Listings will be presented for subjects with AEs, SAEs, AESI, AEs leading to discontinuation, and subjects who die (if any).

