8.2. Handling Partial or Missing Dates on AE, CM, and MH

Partial or complete missing date for AEs, concomitant medication (CM), and medical history (MH) will not be imputed. TEAE and prior and concomitant medication will be determined by using available date information. If available date information cannot determine, refer to section 7.1 for prior and concomitant medication, section 7.4 for TEAE.

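### SAP 7.4 does not say how AEs still ongoing at last contact enter the duration summary; if they are left out, reported duration is biased short

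*Combined protocol and SAP*

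**What the plan says.** SAP 7.4 plans the summary in these words: "The duration of treatment related AE descriptive statistics will be summarized within each PT under each SOC". If a woman has more than one AE coded to the same PT, "the longest AE will be used for that PT for the duration descriptive statistics". SAP 3.1 fixes the statistics: "All continuous variables will be summarized with observed count, mean, standard deviation, median, minimum, and maximum value". No time-to-event method is named for AE duration. Protocol Amendment 2, section 17.6, adds only that "AE duration will be summarized using descriptive statistics by treatment group".

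On dates, SAP 8.2 states: "Partial or complete missing date for AEs, concomitant medication (CM), and medical history (MH) will not be imputed". It sends the reader back to SAP 7.4 for TEAE classification, and SAP 7.4 deals with missing or partial onset dates only. SAP 7.1, by contrast, has a rule for medications with a missing end date.

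On follow-up, Protocol Amendment 2, section 14.5.1, says: "All ongoing AEs must be followed until resolution or for 30 days after" the last study visit. SAP 1.1 plans three-monthly observation for up to 1 year in each treated quadrant. Protocol section 12.5 gives a shorter path: "At the time of study termination, ongoing subjects receiving treatment will be followed through the Day 71 visit".

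**The concern.** An AE that is unresolved when its follow-up stops has a start date and no end date. Its duration is known only to exceed the time observed. A table of means, medians and maxima cannot hold such a value unless the plan says how, and the plan is silent. The programmer must choose between omitting the event, cutting it at last contact, and censoring it. With no end date to subtract from, and imputation ruled out, omission is the easiest outcome. Cutting at last contact and taking a plain mean is also biased short, though less so.

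The rule of one value per woman adds a second effect. If her ongoing event has no duration, her longest event becomes a resolved one. She stays in the count with a shorter value, so the count would not reveal the loss.

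Long-term safety is the primary objective, and protocol sections 8.3.1.1 to 8.3.1.3 describe local reactions in the earlier studies partly by how fast they resolved. A duration table that leaves out unresolved events is weakest on the cases that would qualify that description.

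**Working it through.** The plan gives no AE duration or share of ongoing AEs for this study, so there is no figure to reproduce. The check has two parts: what the text permits, and how large the effect could be under stated assumptions.

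**Text.** Duration needs a start and an end. SAP 8.2 supplies no end date, SAP 7.4 has no cut-off or censoring rule, and SAP 3.1 has no censored method. Followed literally, an ongoing AE yields no value.

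**Cut-offs, counted from the Day 43 session.**
- Day 71 visit: 71 − 43 = 28 days.
- Day 71 plus 30 days of AE follow-up (Day 101): 28 + 30 = 58 days.
- Day 360 plus 30 days (Day 390): 390 − 43 = 347 days.

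**One event from the last session.** Assume an exponential duration with mean m. The 18 days is the mean for local events in the pilot study (protocol section 8.3.1.1); the means of 30 and 60 days and the exponential shape are assumptions.
- Share ongoing at T: q = exp(−T/m).
- Mean among resolved: m − T·q/(1 − q).
- Example, m = 18 and T = 58: q = exp(−58/18) = 0.0399; 18 − 58 × 0.0399/0.9601 = 15.6 days.

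| m (days) | T (days) | Ongoing | Mean among resolved (days) |
|---|---|---|---|
| 18 | 28 | 21.1% | 10.5 |
| 18 | 58 | 4.0% | 15.6 |
| 18 | 347 | 0.0% | 18.0 |
| 30 | 58 | 14.5% | 20.2 |
| 30 | 347 | 0.0% | 30.0 |
| 60 | 58 | 38.0% | 24.4 |
| 60 | 347 | 0.3% | 58.9 |

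**Longest of three events.** Assume one independent event of the PT per session (Days 1, 22 and 43). The true mean of the longest is m × (1 + 1/2 + 1/3): 33 days for m = 18 and 110 days for m = 60. Simulated means:

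| m (days) | T (days) | Longest with an end date | Ongoing cut at last contact |
|---|---|---|---|
| 18 | 58 | 29.8 | 32.1 |
| 18 | 347 | 33.0 | 33.0 |
| 60 | 58 | 45.2 | 69.5 |
| 60 | 347 | 107.7 | 109.6 |

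**A persistent minority.** Here most events follow a gamma distribution (shape 4, mean 18 days) and a share p last 30 days plus an exponential with mean 150. Both p and the persistent distribution are assumptions. In 200,000 simulated women with three events each, the longest resolved event per woman gives:

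| p per event | True mean (days) | Reported, Day 101 | Reported, Day 390 | True median (days) | Reported median, Day 101 |
|---|---|---|---|---|---|
| 0% | 26 | 26 | 26 | 25 | 25 |
| 5% | 48 | 27 | 41 | 26 | 25 |
| 10% | 70 | 28 | 55 | 29 | 25 |
| 20% | 109 | 29 | 81 | 40 | 25 |

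Women with a reaction over 90 days are truly 10%, 19% and 35% for p = 5%, 10% and 20%; under 1% would show at Day 101. In that worst case (p = 20%, Day 101) only 0.3% of women leave the table altogether; the rest stay with a shorter event.

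**The case against.** A reader might infer that the SAP excludes ongoing AEs and therefore will report resolution times that are too short. The documents do not say that. SAP 7.4 speaks of the longest AE without requiring an end date. SAP 8.2 concerns missing and partial dates and does not mention ongoing events, which can be held as a recorded status. On a plain reading, an ongoing event could rank as the longest. This stands: exclusion is the likely default under a silent text, not a stated rule.

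Taking the longest event per woman also raises the summary. With m = 18, every three-event figure above exceeds the 18-day per-event mean. This stands too: the rule shortens the result only when a resolved event replaces a longer ongoing one.

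The Day 101 cut-off is not the planned course for most women. It applies mainly to those still in treatment when the study terminates, or who leave near Day 71; planned observation runs to about a year. The persistent shares are harsh as well: 20% per event means 1 − 0.8³ = 49% of women with a persistent reaction, whereas the protocol reports resolution within 3 weeks in one earlier study and, for the majority of AEs, before the next session in another. The larger differences are therefore an upper illustration, not an expectation.

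The SAP also contains durability visits to Day 720 that Amendment 2 lacks, so a later protocol version may govern AE follow-up. All AEs are listed, and injection-site reactions are a separate safety endpoint. The listings keep individual ongoing events visible, but they do not correct the summary statistic.

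**Conclusion.** The point holds as a gap with a known direction and an unknown size. The plan has no rule for AEs ongoing at last contact. Omitting them, or cutting them at last contact and taking a plain mean, biases the duration summary short.

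If nearly all reactions resolve within weeks, the bias is negligible: none at Day 390 with an 18-day mean, and 29.8 against 33 days for the longest event at Day 101. It becomes material when short follow-up and persistent reactions coincide, for example 27 against 48 days when 5% of events persist and follow-up ends at Day 101. With follow-up to Day 390 the same case gives 41 against 48. Medians move much less: 25 against 26 days in that case at Day 101. All these sizes rest on assumed duration distributions, independent events and one event per session.

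The documents do not support saying that the SAP drops persistent reactions by rule, or that reported duration will be short by any particular amount. This is a cheap improvement to a descriptive safety table.

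**What to change.** In SAP 7.4:

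- Treat an AE ongoing at last contact as right-censored at that date.
- When choosing the longest event per woman and PT, let an ongoing event take precedence over a shorter resolved one.
- Report the Kaplan-Meier median and quartiles of duration for the common treatment-related PTs.
- Print the number and percentage still ongoing at last contact beside every duration.
- Keep the existing descriptive table, labelled as covering resolved events only.

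Add a sentence to SAP 8.2 that an ongoing AE is not a missing date and is handled under SAP 7.4. Restricting Kaplan-Meier to the common PTs avoids curves built on a handful of events; for the rest, the count of ongoing events is enough.

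The cost is some SAP wording and one extra table, and the reported duration may look less favourable. No new data collection and no change to clinical management are involved.

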7.5. Vital Signs

Descriptive statistics for vital signs (body weight, body mass index [BMI], systolic and diastolic blood pressure, pulse rate, respiratory rate, and temperature) and their changes from baseline at each visit and at the end of treatment visit will be presented.

Vital sign values are potentially clinically important (PCI) if they meet both the observed value criteria and the change from baseline criteria. The criteria for PCI vital sign values are detailed

in [Appendix A](#). The baseline in PCI rules refers to the latest vital sign assessment values before the first treatment in study EN3835-202.

A listing of all subjects with PCI vital signs will also be provided.

7.6. Clinical Laboratory Parameters

Table 6 lists all testing parameters for clinical laboratory in this study.

Descriptive statistics for clinical laboratory values in International System of Units (SI) and changes from baseline will be presented for each clinical laboratory parameter.

Table 6: Clinical Laboratory Parameters

Hematology	Clinical Chemistry	Urinalysis
Hematocrit	Blood urea nitrogen	Specific gravity
Hemoglobin	Creatinine	Ketones
Red blood cell count	Total bilirubin	pH
Red blood cell morphology	Alanine aminotransferase (ALT)	Protein
White blood cell count	Aspartate aminotransferase (AST)	Blood
Neutrophils	Alkaline phosphatase	Glucose
Lymphocytes	Sodium	
Monocytes	Potassium	
Basophils	Calcium	
Eosinophils	Chloride	
Platelets	Phosphate	
	Serum bicarbonate	
	Uric acid	
	Total cholesterol	
	Total protein	
	Glucose	
	Triglycerides	
	Albumin	

The number and percentage of subjects with PCI post-baseline clinical laboratory values will be tabulated. The criteria for PCI laboratory values are detailed in [Appendix A](#). A listing of all subjects with PCI laboratory values will also be provided.

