11.2.1. Subject Inclusion Criteria for Treatment

To qualify for treatment in the study a subject must:

1. Voluntarily sign and date an informed consent agreement
2. Have participated in and completed the double-blind study EN3835-201
3. Be a female ≥ 18 years of age
4. At Screening B visit, have at least 1 quadrant with:
 - a. a score of 3 or 4 (moderate or severe) as reported by the subject (PR-PCSS), and
 - b. a score of 3 or 4 (moderate or severe) as reported by the Investigator (CR-PCSS), and
 - c. a Hexsel CSS score no greater than 13
5. Be willing to apply sunscreen to the selected treatment quadrant before each exposure to the sun while participating in the study (ie, Screening B through end of study)
6. Be judged to be in good health, based upon the results of a medical history, physical examination, and laboratory profile at Screening B

7. Have a negative urine pregnancy test at Screening B and before injection of study drug and be using an effective contraception method (eg, abstinence, intrauterine device [IUD], hormonal [estrogen/progestin] contraceptives, or double barrier method) for at least 1 menstrual cycle prior to study enrollment and for the duration of the study; or be menopausal defined as 12 months of amenorrhea in the absence of other biological or physiological causes, as determined by the Investigator; or post-menopausal for at least 1 year; or be surgically sterile.
8. Be willing and able to cooperate with the requirements of the study
9. Be able to read, complete and understand the patient-reported outcomes rating instruments in English

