3.2. Baseline Considerations

The baselines for all cellulite assessments, including CR-PCSS, PR-PCSS, and Hexsel CSS will be the observed values at visit Day 1 before subjects receive EN3835 treatment. If the values at Day 1 are missing, the values at Screening will be used for those assessments. For observation phase before EN3835 treatment in current study, the baselines will be the values at Day 1 for study EN3835-201. The reference values will be the observed scores at Day 71 in study EN3835-201 for those assessments. For the potentially clinically importance (PCI) calculation for vital sign values, the baseline refers to the latest vital sign assessment values before the first treatment in study EN3835-202.

All baselines for safety measures, ie, vital signs, clinical laboratory parameters, will use the latest values before subjects receive the first treatment in study EN3835-202.

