APPENDIX A. PCI CRITERIA

Laboratory Values

Test	Low	High
Platelets ($10^9/L$)	≤ 100	≥ 650
Hemoglobin (g/L)	≤ 100	≥ 190
Hematocrit	≤ 0.3	≥ 0.6
ALT	---	$\geq 3 \times ULN$
AST	---	$\geq 3 \times ULN$
Creatinine ($\mu\text{mol}/L$)	---	≥ 300
BUN (mmol/L)	---	≥ 12

Vital Signs

Test	Low	High
Systolic Blood Pressure	≤ 90 mmHg and decrease ≥ 20 mmHg from baseline	≥ 180 mmHg and increase ≥ 20 mmHg from baseline
Diastolic Blood Pressure	≤ 50 mmHg and decrease ≥ 15 mmHg from baseline	≥ 105 mmHg and increase ≥ 15 mmHg from baseline
Pulse Rate	≤ 50 bpm and decrease ≥ 15 bpm from baseline	≥ 120 bpm and increase ≥ 15 bpm from baseline
Respiratory Rate	≤ 8 brpm and decrease ≥ 7 brpm from baseline	≥ 25 brpm and increase ≥ 7 brpm from baseline
Temperature	---	$\geq 38.3^\circ\text{C}$ and increase $\geq 1.1^\circ\text{C}$ from baseline

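### The laboratory PCI count in SAP 7.6 pools women already beyond a limit at baseline with new abnormalities; it should be split by baseline status

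*Combined protocol and SAP*

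**What the plan says.** SAP 7.6 plans three laboratory outputs:

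- summaries: "Descriptive statistics for clinical laboratory values in International System of Units (SI) and changes from baseline will be presented for each clinical laboratory parameter";
- the PCI table: "The number and percentage of subjects with PCI post-baseline clinical laboratory values will be tabulated", with the criteria in Appendix A;
- a listing: "A listing of all subjects with PCI laboratory values will also be provided".

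Appendix A sets laboratory limits for seven tests: platelets, hemoglobin, hematocrit, ALT, AST, creatinine and BUN. Each is a fixed threshold (for example hemoglobin ≤100 or ≥190 g/L, BUN ≥12 mmol/L) or a multiple of the upper limit of normal (ALT and AST ≥3 × ULN). No laboratory row has a baseline or change term.

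Vital signs are handled differently. SAP 7.5 says "Vital sign values are potentially clinically important (PCI) if they meet both the observed value criteria and the change from baseline criteria", and every vital-sign row in Appendix A follows that form. The low limit for systolic pressure, for instance, is "≤ 90 mmHg and decrease ≥ 20 mmHg from baseline".

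A laboratory baseline already exists. SAP 3.2 says that baselines for safety measures "will use the latest values before subjects receive the first treatment in study EN3835-202". The PCI rule for laboratory values does not use it.

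The protocol has the same asymmetry. Section 17.6.5 asks for value plus change for vital signs. Section 17.6.6 counts post-baseline laboratory values with no such condition and leaves the criteria to the SAP.

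**The concern.** In SAP 7.6, the term post-baseline restricts when the sample was taken. It says nothing about where the subject started. A stable abnormality that was present before the first EN3835-202 injection therefore enters the same number and percentage as one that appeared afterwards.

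Long-term safety is the primary objective, and laboratory testing is a listed safety endpoint. The treatment phase is open-label and not randomized (SAP 1.5), so no concurrent control rate shows how much of the count is background. Scheduled laboratory samples for treated women are few: Screening B and Day 71 (SAP Table 3), then Day 360 or end of study (SAP Table 2). The investigator may order extra tests (Protocol 14.7). With so few samples, the comparison with each woman's own baseline matters, and the table does not make it.

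**Working it through.** The plan gives no expected PCI rate, so there is no stated figure to reproduce. The check is to apply the Appendix A rules as written to hypothetical pairs of values.

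**Rules, from Appendix A**

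- Hemoglobin (g/L): counted if post ≤100 or post ≥190.
- Platelets (10⁹/L): counted if post ≤100 or post ≥650.
- BUN (mmol/L): counted if post ≥12.
- Systolic pressure (mmHg): counted if post ≤90 and base − post ≥20, or if post ≥180 and post − base ≥20.
- Pulse (bpm): counted if post ≤50 and base − post ≥15, or if post ≥120 and post − base ≥15.

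The baseline value appears in the two vital-sign rules and in none of the laboratory rules.

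**Applied to hypothetical pairs**

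| Test | Baseline | Post | Status | Counted as PCI? |
|---|---|---|---|---|
| Hemoglobin | 98 | 98 | unchanged | yes |
| Hemoglobin | 95 | 99 | improved | yes |
| Platelets | 95 | 97 | slightly improved | yes |
| BUN | 12.5 | 12.1 | slightly improved | yes |
| Hemoglobin | 120 | 98 | new | yes |
| Systolic pressure | 88 | 88 | unchanged | no |
| Pulse | 49 | 48 | change of 1, needs 15 | no |
| Systolic pressure | 115 | 88 | new (fall of 27) | yes |

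The vital-sign rule separates new from pre-existing values. The laboratory rule does not. A carried-over subject is counted only if her value is still beyond the limit after baseline.

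**Can the size be fixed from the documents?** Let q be the proportion PCI at baseline, s the proportion of those who stay PCI, and i the rate of new PCI among the rest. The share of the tabulated count that is carried over is

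q·s / (q·s + (1 − q)·i).

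The documents give none of these three quantities. The figures below are assumptions, for scale only: s = 70%, q from 0.5% to 3%, i from 0.5% to 1%.

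- q = 0.5%, i = 1%: 0.0035 / (0.0035 + 0.00995) = 26%.
- q = 3%, i = 0.5%: 0.021 / (0.021 + 0.00485) = 81%.
- If screening leaves nobody PCI at baseline (q = 0), the share is 0%.

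The answer depends entirely on the assumed inputs. The calculation shows only that when PCI values are rare, a few carried-over cases can be a visible part of the count.

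**The case against.** The strongest case for leaving the plan alone has five parts.

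- **The label is accurate.** The table reports post-baseline PCI values and does not call them treatment-emergent. A woman at 98 g/L on Day 71 does have such a value. This stands: the SAP makes no false claim. The count is simply less informative than it could be.
- **Other outputs address emergence.** Changes from baseline are summarized for the laboratory parameters, and Table 6 lists 35 of them against seven tests in Appendix A. PCI subjects are listed. Abnormal results judged clinically significant are recorded as adverse events (Protocol 14.7), and SAP 7.4 requires a treatment-emergent event to start on or after treatment start. So a reader who inferred that the PCI table is the main laboratory safety summary would go too far. These outputs still do not split the tabulated number: the change summaries are at group level, and the SAP does not say whether the listing shows baseline status.
- **Screening makes the problem rare.** Treatment inclusion criterion 6 (Protocol 11.2.1) requires a woman to "Be judged to be in good health, based upon the results of a medical history, physical examination, and laboratory profile at Screening B", and several Appendix A limits are extreme, such as creatinine ≥300 µmol/L. This lowers the frequency. It does not exclude the problem, because the criterion is a judgement with no numeric limit tied to Appendix A.
- **The SAP follows the protocol.** Sections 17.6.5 and 17.6.6 already differ in the same way, so this is not a contradiction between documents.
- **Over-counting is the cautious direction for safety.** This stands as an argument against removing anyone from the count. It is no argument against showing baseline status beside it.

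**Conclusion.** The point holds as a small improvement to one table. SAP 7.6 counts laboratory PCI values without reference to the baseline that SAP 3.2 defines, so unchanged or improved pre-existing abnormalities are pooled with new ones. The counting rule is certain from the text. Its numerical effect is unknown and probably small.

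Three stronger readings are tempting, and the documents do not support them.

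- **A predicted number of miscounted women.** No baseline prevalence is given. The 333 in Protocol 17.1 is expected enrolment, not the number treated, and treatment is optional.
- **Excluding women who were PCI at baseline.** That would drop real worsening from the count, for example hemoglobin falling from 99 to 75 g/L.
- **Treating every carried-over value as older than EN3835.** The SAP 3.2 baseline precedes the first EN3835-202 injection. For women given placebo in EN3835-201, that is before any EN3835 in these two studies. For women given active drug there, it follows an earlier course, so an abnormality present at this baseline may have begun after exposure.

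**What to change.** In SAP 7.6, keep the overall PCI count as it is and add a split for each Appendix A test:

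1. Not PCI at the SAP 3.2 baseline, PCI afterwards.
2. Already PCI at that baseline and PCI afterwards, with each woman's baseline and worst post-baseline value shown so that worsening stays visible.
3. PCI afterwards with no baseline under SAP 3.2. Observation-only women, for example, never have a first EN3835-202 treatment to anchor it.

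Add a footnote that, for women treated with EN3835 in EN3835-201, this baseline follows earlier exposure, so the second row is not a count of abnormalities that predate the drug.

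The cost is a sentence or two in SAP 7.6 and a column or a few rows in an existing table, settled before database lock. It needs no new samples or visits and no change to the Appendix A limits.
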